4.4.3 Lost to Follow-Up

A subject should only be designated as lost to follow-up if the study site personnel are unable to establish contact with the subject or parent/caregiver after 3 documented attempts via 2 different methods (eg, phone, text, e-mail, certified letter). These efforts should be documented in the subject's source documents.

4.4.4 Subject Replacement

Since this is a rollover study of subjects who have participated in at least 1 prior study with AR101, no subject who discontinues AR101 treatment early will be replaced.

5 STUDY TREATMENT

5.1 Formulation, Packaging, and Labeling

AR101 is characterized peanut allergen in the form of peanut flour, formulated with a bulking agent (maize starch, microcrystalline cellulose, and other excipients to prevent clumping) and a flow agent in premeasured graduated doses. The capsules used in the Initial Escalation Period and Up-Dosing Period of this study currently include the following strengths: 0.5, 1, 10, 20, and 100 mg each of peanut protein. AR101 is characterized by high performance liquid chromatography and by specific enzyme-linked immunosorbent assay for key allergenic proteins to demonstrate stability and lot-to-lot consistency.

AR101 capsules will be provided in prepackaged dosing kits. For the escalation periods, each individual kit will contain 21 daily doses at a given dose level, enough to supply 2 weeks of dosing plus a 7-day overage to accommodate potential visit scheduling issues.

For Initial and Extended Maintenance Period dosing, a 300 mg AR101 dose will be provided in sealed, foil-laminate sachets (1 sachet/day). Sachets will be provided in kits containing 35 individual doses.

All AR101 will be packaged and labeled at the central packaging facility. AR101 will then be shipped to a drug depot where it will be labeled and inventoried for shipment to the clinical sites. AR101 will be dispensed, according to subject identification number using a web-based interactive response system (IXRS), directly at the study site or the study site pharmacy, according to site-specific institutional policies. AR101 will then be distributed to each subject or parent/caregiver by study site personnel.

AR101 will be stored in a secure location at each study site and kept refrigerated between 2°C and 8°C. Study site personnel will maintain temperature logs for all refrigerators storing

study drug for the duration of the study. Temperature excursions may be allowed with specific instructions from the sponsor and as described in the pharmacy manual.

Dispensation of study product may be affected by a pandemic, epidemic, or other emergency not related to the study as described in Appendix 12.

5.2 Preparation, Administration, and Dosing

All doses scheduled to be administered on clinic visit days will be taken at the clinic. Subjects should withhold their daily home AR101 dose on in-clinic dosing days but should take all other prescribed medications as scheduled. Doses will be administered in the clinic under the direct supervision of an appropriately qualified healthcare provider and the oversight of a physician. This dose, intended for in-clinic administration, will be removed from the dosing kit for the assigned dose level. Once a dose is removed from the dosing kit, the kit must be dispensed to the subject or held at the site for documented destruction or return to the sponsor's designee (as instructed); dosing kits once opened cannot be used for any other dosing interval or any other subject.

At each clinic visit in the Up-Dosing, Initial Maintenance, and Extended Maintenance Periods, the subject or parent/caregiver will receive a kit of capsules or sachets to be taken at home according to the current dose level. The subject or parent/caregiver will be instructed to store the dosing kit in the refrigerator at all times other than when it is removed to obtain the daily dose, and to bring all unused capsules/sachets back to the clinic at the next visit. For Treatment Pathways 4 and 5 only, the parent/caregiver will be instructed to record the capsules/sachets taken at home in a diary log.

In exceptional circumstances when a subject is unable to return to the clinic for the next scheduled visit (eg, travel, holidays) and continued dosing is necessary, an additional dosing kit may be dispensed on a case-by-case basis after submission of a documented request and medical monitor approval. One additional dosing kit may be dispensed to continue the current dose level if there are no safety concerns in the opinion of the investigator and medical monitor (eg, the dose level is tolerated, no intercurrent illnesses) and the subject will have access to appropriate emergency medical services as needed. Up-dosing is not allowed until the next clinic visit.

Procedures for preparation and administration of doses given in the clinic or at home are the same. Dose preparation will be completed by the subject or by a supervising adult. For in-clinic dosing, dose preparation may be performed by clinic staff or by the subject or parent/caregiver under the direct supervision of clinic staff for the purpose of teaching and reinforcing training. The capsules should be pulled apart and gently rolled between finger and thumb and then lightly tapped on each half of the capsule to ensure full delivery of contents. When using a sachet, the sachet is to be cut over the vehicle food and the entire contents emptied into the food. The sachet should then be gently squeezed and shaken to ensure full delivery of contents. The contents of the capsules/sachets will be mixed with a vehicle food, such as apple sauce, yogurt, pudding, or other palatable, age-appropriate food.

Care must be taken not to inhale the powder as this could provoke worsening of asthma or induce an allergic reaction. AR101 may not be added to food heated above room temperature before consumption. The vehicle food must be one to which the subject is not allergic. The volume of the vehicle food should be such that the entire AR101 dose can be consumed in a few spoonfuls. The AR101 dose should be consumed as promptly after mixing as practicable. If not consumed within 4 hours of mixing into a vehicle, the AR101-vehicle food mixture must be discarded and a new dose mixed prior to consumption. If preparing a new dose is not feasible (eg, due to limited supply), the AR101-vehicle food mixture may be stored for up to 24 hours under conditions appropriate for the vehicle food in which the AR101 was mixed. If there is a delay of more than 24 hours in consumption, this AR101-vehicle food mixture must be discarded and the process restarted with a new AR101 dose. It is recommended that each dose of AR101 be taken at a consistent time (within a 4-hour period) each day that the dose is to be taken. An interval of ≥ 8 hours should pass between doses. Per investigator judgment, a home dose may be split into 2 portions for tolerability, as further discussed in Section 6.9.3.

The following precautions must be followed:

- Except for on days with in-clinic dosing, the daily home dose will be taken as part of a meal or heavy snack. The subject must have other food (besides the matrix vehicle) in the stomach before taking the dose.
- Dosing at the evening meal is recommended for children so the subject can be observed and supervised in the home setting by their parent(s)/caregiver(s) for several hours after dosing.
- Subjects are to avoid activities likely to increase allergic reactivity (eg, exercising or taking hot showers or baths within 3 hours after dosing).
- Dosing should also not occur within 2 hours of bedtime.
- If a subject has engaged in strenuous exercise before the planned dosing time, dosing must be delayed until any signs of a hypermetabolic state (eg, flushing, sweating, rapid breathing, and/or rapid heart rate) have abated.
- For subjects aged 1 to < 4 years: In case of illness with or without fever, or symptoms such as wheezing, worsening asthma, vomiting, or diarrhea, the parent/caregiver is to withhold the dose of study product from the subject and notify the study site of the symptoms and for possible dose adjustments.

Except as may be necessary in the course of treating an AE, it is crucial that the subject takes the doses according to their assigned schedule. No attempt should be made to make up for a missed dose if greater than 6 hours have elapsed since the usual time of dosing.

Directions for the administration and dispensation of study product may be affected by a pandemic, epidemic, or other emergency not related to the study as described in Appendix 12.

5.3 Postdose Monitoring at the Clinic

All subjects will be monitored for AEs including allergic reactions following dosing in the clinic. The time period for monitoring the subject is dependent on the severity of any symptoms that occur (Section 8.2.2.1) and the study period (Section 7).

The occurrence of any severe symptoms that include hypoxia, hypotension, change in mental status, grade 3 severe anaphylaxis (as defined in Appendix 8), or intensive therapy (to be determined by the investigator, but may include such interventions as IV epinephrine, intubation, or admission to an intensive care unit) for an allergic reaction anytime must be discussed with the medical monitor, and the subject must discontinue dosing in the study.

5.3.1 Screening/Baseline Visit (Treatment Pathways 1, 2, and 4)

Subjects who are administered AR101 at the Screening/Baseline visit must be observed for at least 90 minutes after dosing. Vital signs will be measured and signs and symptoms of allergic reaction assessed 15 to 30 minutes after the dose and approximately every 30 minutes thereafter until the end of observation. The observation period may be extended as described in Section 5.3.2.1.

5.3.2 Initial Dose Escalation Days (Treatment Pathways 3 and 5)

5.3.2.1 Day 1

Vital signs will be measured and signs and symptoms of allergic reaction assessed at 15 minutes after each dose and just prior to administration of the next dose. Doses will be administered at 20- to 30-minute intervals, but if the dose interval is extended because of symptoms, vital sign measurement and allergic sign/symptom assessment will then occur at 30-minute intervals and for the duration of the postdose observation period. Each subject will be observed for at least 90 minutes after the last dose; vital signs will be measured and signs and symptoms of allergic reaction assessed 15 to 30 minutes after the dose and approximately every 30 minutes thereafter until the end of observation.

[figure not shown]
The postdose observation period will be conducted as follows:

- If dosing is completed with no symptoms detected before 90 minutes of observation after the last dose, the subject may be sent home from the clinic.
- If a subject exhibits **mild symptoms**, the observation period will be extended to a minimum of 1 hour after resolution of the symptoms. The subject may continue dosing in the study.
- If a subject experiences **moderate symptoms**, the observation period will be extended to a minimum of 2 hours after resolution of the symptoms. The subject will discontinue dosing in the study.
- If a subject experiences **severe symptoms**, the observation period will be extended to a minimum of 3 hours after resolution of the symptoms and will occur either at the

clinic or at an emergency facility, as appropriate. The subject will discontinue dosing in the study.

The actions to be taken for allergic symptoms that occur during Escalation Day 1 are shown in Figure 4.

Figure 4: Schematic for Initial Escalation Day 1

5.3.2.2 Day 2

Subjects must be observed for at least 90 minutes after dosing. Vital signs will be measured and signs and symptoms of allergic reaction assessed 15 to 30 minutes after the dose and approximately every 30 minutes thereafter until the end of observation. The observation period will be extended as necessary as described in Section 5.3.2.1.

5.3.3 Up-Dosing Period (Treatment Pathways 2, 3, and 5)

Subjects must be observed for at least 90 minutes after dosing. Vital signs will be measured and signs and symptoms of allergic reaction assessed 15 to 30 minutes after the dose and approximately every 30 minutes thereafter until the end of observation. The observation period will be extended as necessary as described in Section 5.3.2.1.

5.3.4 Initial Maintenance Period (Treatment Pathways 2, 3, and 5) and Extended Maintenance Period (All Treatment Pathways)

Subjects in Treatment Pathways 1, 2, and 3 must be observed for at least 30 minutes after dosing with vital sign measurements and assessment for signs and symptoms of allergic reaction. Postdose vital signs will be measured and signs and symptoms of allergic reaction assessed 15 to 30 minutes postdose, and at 15- to 30-minute intervals thereafter if the postdose observation period is prolonged beyond the requisite 30 minutes.

Subjects in Treatment Pathways 4 and 5 must be observed for at least 90 minutes after dosing. Vital signs will be measured and signs and symptoms of allergic reaction assessed 15 to 30 minutes postdose, and approximately every 30 minutes thereafter until the end of observation. The postdose observation period during maintenance treatment may be shortened to approximately 30 minutes if no allergy symptoms occurred during the previous 3 maintenance visits.

The procedure for monitoring subjects for safety after in-clinic dosing is the same as for other visits (Section 5.3.2.1), except that the initial period of required postdose observation may be shortened to 30 minutes for tolerated doses.

5.4 Dosing After Missed, Withheld, or Delayed Doses

A dose can be taken up to 6 hours after the usual time of dosing. If more than 6 hours has elapsed, the dose should not be taken and will be considered as missed.

[figure not shown]
Missed doses of study product can pose a significant risk to subjects anytime during the study, and the greatest risk is considered to be during up-dosing. Missing 1 dose or 2 consecutive doses due to medical reasons (eg, intercurrent illness, AE) or for nonmedical reasons (eg, forgetting, intentional) cannot be avoided at times and is allowed. Missing 3 or more consecutive doses for medical reasons with investigator awareness is allowed and requires reinitiation of dosing under medical supervision. Missed doses for nonmedical reasons are allowed if the total number of missed doses between study visits is not excessive (ie, > 80% of dispensed doses were taken between study visits). Procedures and allowance for missed consecutive doses of study product during up-dosing and maintenance are described in the following sections.

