7.5.3.2 End Up-Dosing Visit

The following procedures will be performed before AR101 is administered in the clinic:

- TRACK questionnaire (for subjects aged 1 to < 5 years with asthma only; completed by the parent/caregiver)
- C-ACT (for subjects aged ≥ 5 years with asthma only) (complete before PEF)
- Weight, height
- Vital signs
- PEF (for subjects aged ≥ 4 years) (should be measured at approximately the same time of day at each visit assessment)
- Asthma evaluation (for subjects with asthma only)
- Abbreviated physical examination
- Food allergen exposure update
- Monitoring and recording of AEs, including allergy symptoms

- Concomitant medication review
- Diary log review (and dispensing of new diary log, if needed)
- Return of unused AR101
- AR101 dosing compliance check
- Completion of questionnaires:
 - FAQLQ and FAIM
 - FAQL-PB

After completion of these procedures, AR101 will be administered in the clinic as instructed in Section 3.2.3.2 and Section 5.2. Subjects will be monitored as instructed in Section 5.3.3.

The following procedures will be performed before discharge from the clinic:

- Monitoring and recording of AEs, including allergy symptoms
- Peanut allergy training
- AR101 dispensing
- Home dosing instruction (Section 5.2)

Site staff will contact the subject's parent/caregiver by telephone the next day (may be within 2 days if next day is not feasible) to monitor compliance with AR101 dosing, enquire if any AEs (including allergy symptoms, GI symptoms, and accidental/nonaccidental food allergen exposure) occurred after the subject left the clinic, and to provide assistance in recording and management of events.

7.5.4 Initial Maintenance Period (Visits Every 4 Weeks Until End of Initial Maintenance Visit)

During the Initial Maintenance Period, clinic visits will occur every 4 weeks ± 3 days until the End of Initial Maintenance visit, when the subject completes an overall total of approximately 12 months of treatment (including initial dose escalation, up-dosing, and maintenance treatment).

Subjects should withhold their daily home dose of AR101 on days the dose is administered in the clinic but should take all other prescribed medications as scheduled.

The guidelines for dose escalation and reduction are the same as for the Up-Dosing Period (Section 7.5.3).

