4. ANALYSIS POPULATION

The following analysis population will be defined for this study:

Safety Population: The Safety Population will consist of all subjects who receive AR101 during ARC008. The Safety Population will be used for all analyses.

5. **PROTOCOL DEVIATIONS**

Any change, divergence, or departure from the study design or procedures constitutes a protocol deviation. All protocol deviations will be reported on a specific case report form (CRF) as follows:

- Inclusion Criteria
- Exclusion Criteria
- Received Incorrect Study Treatment
- Informed Consent Form (ICF)
- SAE Not Reported
- Visit Out Of Window
- Missed Study Visit
- Procedure Not Per Protocol
- Prohibited Concomitant Medication
- Lab Sample Missed
- Study Drug Compliance
- Other, Specify

These protocol deviations will be reviewed prior to database lock and their categorization as major or minor will be determined prior to database lock. All protocol deviations, both major and non-major, will be listed and included in the study report.

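### Section 5.4 judges nonmedical missed doses against doses dispensed, which include planned overage, so in Pathway 2 and 3 up-dosing its 80% condition cannot be met at any in-window visit

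*Protocol*

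**What the plan says.** Protocol Section 5.4 makes three statements in sequence. One missed dose, or two in a row, is accepted whatever the reason. Three or more in a row for medical reasons is accepted if the investigator knows and dosing restarts under supervision. Missed doses for nonmedical reasons are then accepted if their total between visits is not excessive. The section defines that condition (with an ie, so not as an example) as "> 80% of dispensed doses were taken between study visits".

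Section 5.1 describes the supply. For capsules, "each individual kit will contain 21 daily doses at a given dose level, enough to supply 2 weeks of dosing plus a 7-day overage". For maintenance, at one sachet a day, "Sachets will be provided in kits containing 35 individual doses". Under Section 5.2 the subject or caregiver at each clinic visit "will receive a kit of capsules or sachets to be taken at home according to the current dose level", and unused doses come back at the next visit. The clinic dose comes from the same supply: "This dose, intended for in-clinic administration, will be removed from the dosing kit for the assigned dose level".

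Section 5.7 calls for compliance to be checked but gives no formula. SAP Section 5 lists "Study Drug Compliance" as a deviation category, with no threshold or denominator. Neither document redefines dispensed doses as scheduled doses.

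**The concern.** A ratio meant to show whether too many doses were missed should be close to 100% when none were. Here the denominator contains doses that were never due, so the ratio falls short of 100% by an amount set by kit size and visit date, before any dose is missed. The shortfall is largest in up-dosing, the period in which Section 5.4 says missed doses carry the greatest risk.

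At stake is whether a site can apply the allowance at all. If the condition cannot be met in an interval, it permits no nonmedical misses there, although the same section has just accepted one or two. Two sites could then handle the same subject differently, one reading the percentage literally and the other reading it as a share of doses due.

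**Working it through.** **Inputs.** The limit is strictly above 80% of dispensed doses (Section 5.4). Kits hold 21 capsule doses or 35 sachets (Section 5.1). Visit intervals are:
- Up-dosing: 2 weeks ±2 days in Pathways 2 and 3 (Sections 7.2.2 and 7.3.3); 2 weeks ±3 days in Pathway 5 (Section 7.5.3).
- Initial Maintenance: in Pathway 5, "clinic visits will occur every 4 weeks ± 3 days until the End of Initial Maintenance visit" (Section 7.5.4); in Pathways 2 and 3, 8 weeks ±1 week (Sections 7.2.3 and 7.3.4).
- Extended Maintenance: 3 months ±2 weeks, taken as 91 ±14 days.

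**The plan's own figure.** 14 days + 7 days of overage = 21 doses, which agrees with Section 5.1.

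**Formula.** Ratio = (doses due − doses missed) / (kits × doses per kit). The number of kits is the smallest whole number that covers the interval. The clinic dose is counted in both parts because it comes from the kit.

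**Daily dosing, nothing missed:**

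| Interval | Nominal | Earliest in window | Latest in window |
|---|---|---|---|
| Up-dosing, Pathways 2 and 3, one kit | 14/21 = 66.7% | 12/21 = 57.1% | 16/21 = 76.2% |
| Up-dosing, Pathway 5, one kit | 14/21 = 66.7% | 11/21 = 52.4% | 17/21 = 81.0% |
| Initial Maintenance, Pathway 5, one kit | 28/35 = 80.0% | 25/35 = 71.4% | 31/35 = 88.6% |
| Initial Maintenance, Pathways 2 and 3, two kits (assumed) | 56/70 = 80.0% | 49/70 = 70.0% | 63/70 = 90.0% |
| Extended Maintenance, three kits (assumed) | 91/105 = 86.7% | 77/105 = 73.3% | 105/105 = 100.0% |

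**Reading the up-dosing rows.** 80% of 21 is 16.8, so at least 17 doses must be taken. Pathways 2 and 3 have at most 16 due in window. Pathway 5 reaches 17 only on the last day of its window.

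**Counting home doses only** (subtract 1 from both parts) gives 13/20 = 65.0%, 27/34 = 79.4% and 55/69 = 79.7% at the nominal 2-, 4- and 8-week visits. Day 17 in Pathway 5 becomes 16/20 = 80.0%, which no longer passes.

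**With misses that Section 5.4 accepts.** In a 14-day interval, one forgotten dose gives 13/21 = 61.9% and two give 12/21 = 57.1%. As a share of the 14 doses due, the same subjects took 13/14 = 92.9% and 12/14 = 85.7%.

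**Nondaily regimens, illustration only.** The documents do not say how many sachets are dispensed. Over 91 days with nothing missed, the ratios with the fewest whole kits and then with three kits are:
- every other day: 45.5/70 = 65.0%; 45.5/105 = 43.3%
- twice weekly: 26/35 = 74.3%; 26/105 = 24.8%
- weekly: 13/35 = 37.1%; 13/105 = 12.4%
- every other week: 6.5/35 = 18.6%; 6.5/105 = 6.2%

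**The case against.** The strongest reply is that the percentage is a condition for excusing missed doses, so a subject who missed none needs no excuse and an unused spare dose is not a missed dose. That is right. A reader might infer from 66.7% that fully adherent subjects fail the rule, and the text does not support that. What remains is the subject for whom the allowance was written. One forgotten up-dosing dose is accepted in one sentence and excessive under the percentage shortly after. If the percentage is read as covering only misses beyond the first one or two, it still cannot be met at any in-window up-dosing visit in Pathways 2 and 3.

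A reader might also infer that the protocol cannot detect nonadherence. It can, by rules that do not use dispensed doses. Section 4.4.1 (criteria 6 and 7) counts consecutive missed dosing days on daily regimens. Section 3.1.1 counts consecutive missed scheduled doses on nondaily regimens. Section 5.4.2 requires a discussion with the medical monitor when a nondaily dose is more than 3 days late. No section attaches discontinuation or a dose change to the 80% figure.

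A third inference would be that the deviation tables contain false compliance entries. Nothing links the SAP category to Section 5.4, and the documents do not show that sites applied the percentage literally. That effect is conditional.

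Finally, the maintenance figures depend on timing and supply. The exact 80.0% holds only at the nominal visit with the clinic dose counted, and later visits can pass. At 8 weeks it also needs two kits. Section 5.2 speaks of a kit per visit, but one 35-dose kit cannot cover 56 days. Two is therefore the minimum, and more would lower the ratio.

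**Conclusion.** The inconsistency is real and limited. It is firmest in up-dosing, where the kit content and its purpose are both stated: the ratio cannot exceed 80% at any in-window visit in Pathways 2 and 3, and in Pathway 5 it can do so only at day 17 with the clinic dose counted. Section 5.4 therefore conflicts with the overage in Section 5.1 and with its own acceptance of one or two missed doses.

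In Initial Maintenance the on-schedule ratio sits exactly at the limit and fails a strict inequality. This rests on nominal timing and, at 8 weeks, on two kits. Daily Extended Maintenance passes at 91 days on three kits. The nondaily figures rest on an unstated dispensing quantity and carry no weight beyond illustration.

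No study estimate is affected. SAP Section 4 defines only the Safety Population, with no per-protocol set, and SAP Section 9.11 builds exposure from dosing intervals, frequency, and missed and partial doses. The consequence is an allowance that sites cannot apply as written and, only if it was so applied, some compliance deviations that need a second look.

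**What to change.** Sections 5.1 and 5.4 must be reconciled. The sponsor should state in Section 5.4 a denominator that is consistent with the planned overage and with the section's own acceptance of one or two missed doses, and say whether the clinic dose counts and how the rule applies to nondaily regimens. The denominator also determines how many missed doses are tolerated. That choice, the threshold and any clinical action are therefore for the sponsor, and no value is proposed here.

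SAP Section 1.1 places database lock before SAP Version 2, and SAP Section 7.7 says the study ended early, so a text change may come too late to guide dosing. If the percentage was used to record compliance deviations, the study report should state which denominator was used, and those entries should be re-checked. If it was not used, one sentence saying so is enough.

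The cost is a short text correction and possibly some re-checking of recorded deviations. No new data are needed.
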